## 3.4.1.4 Time to Response

Time to response (TTR) is defined as the time from randomization (dose expansion) / the first dose of IP (dose escalation) until the first documentation of objective response. Only subjects who have achieved objective response will be evaluated for TTR. TTR is defined in months as follows:

TTR (months) = (Date of first confirmed disease response – Date of randomization (dose expansion) / the first dose of IP (dose escalation) first dose of IP + 1) / (365.25/12).

The median TTR and its 95% CI will be assessed using the Kaplan-Meier method. An 80% CI for median time *may* also be included.

#### 3.4.1.5 Duration of Response

Duration of response (DR) is defined as the time from the first documentation of a subsequently confirmed objective response until the first documentation of disease progression or death due to any cause, whichever occurs first. Only subjects who have achieved objective response will be evaluated for DR. DR is defined in months as follows:

DR (months) = (Date of PD/death or censoring – Date of first subsequently confirmed disease response + 1) / (365.25/12),

such that date of PD/death or censoring is given in Table 3.2. The median DR and its 95% CI will be estimated using the Kaplan-Meier method. An 80% CI for median time *may* also be included.

#### 3.4.1.6 Progression-free Survival

Progression-free survival (PFS) is defined as the time from randomization (dose expansion) / the first dose of IP (dose escalation) until the first documentation of disease progression or death due to any cause, whichever occurs first, regardless of whether the subject receives subsequent anticancer therapy prior to progression. Subjects who have not progressed at the time of analysis will be censored at the time of the latest date of assessment from their last adequate progression free disease assessment. Censoring rules are presented in Table 3.2. PFS is defined in months as follows:

PFS (months) = (Date of PD/death or censoring – Date of randomization (dose expansion) / the first dose of IP (dose escalation) first dose of IP+1) / (365.25/12)

The median PFS and its 95% CI will be estimated using the Kaplan-Meier method. An 80% CI for median time *may* also be included.

For the expansion phase, the difference in PFS between treatment groups will be tested for significance with a logrank test. The hazard ratio for the two treatment groups with two-sided 95% CI will be estimated by a Cox proportional hazard model controlling for the prespecified stratification factors as explanatory variables in the model. The proportion of subjects progression free and alive at 6 months and associated 95% CI will be estimated using the Kaplan-Meier method.

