### **Dose-expansion Phase**

To evaluate the antitumor activity of MEDI0680 in combination with durvalumab versus nivolumab monotherapy in immunotherapy-naïve subjects with advanced or metastatic ccRCC as based on investigator assessed response using Response Evaluation Criteria in

Solid Tumors Version 1.1 (RECIST 1.1) (Eisenhauer et al, 2009).

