The dose-expansion phase will begin after the dose-escalation phase. Immunotherapy-naïve subjects with ccRCC will be randomized in a 2:1 ratio to either (1) MEDI0680/durvalumab combination therapy or (2) nivolumab monotherapy. Stratification factors will include the Memorial Sloan Kettering Cancer Center (MSKCC) risk group (0 = favorable risk; 1 or 2 = intermediate risk; 3 = poor risk) and PD-L1 expression status ( $\leq$  1% and > 1%). Up to 40 subjects may be randomized in to the MEDI0680/durvalumab combination therapy arm and up to 20 subjects in the nivolumab monotherapy arm based on evaluation of emerging safety and efficacy parameters in the current study as well as other ongoing studies. Interim futility analyses will be performed in a continuous manner using Bayesian Predictive Probability (see Section 4 Interim Analysis).

Figure 2-1 Study Design

ccRCC = clear-cell RCC; CRC = colorectal cancer; MSI = microsatellite instability; MTD = maximum tolerated dose; NSCLC = non-small cell lung cancer; RCC = renal cell carcinoma; SCCHN = squamous cell carcinoma of head and neck.

a Up to a total of 60 subjects with ccRCC will be randomized in a 2:1 ratio to receive either MEDI0680/durvalumab combination therapy or nivolumab monotherapy.

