For the dose-expansion phase, up to approximately 60 subjects (40 subjects in the MEDI0680/durvalumab combination therapy arm and 20 subjects in the nivolumab monotherapy arm) may be randomized at the selected combination dose (ie, MTD or highest protocol-defined dose for each agent in the absence of exceeding the MTD) in a 2:1 ratio. Assuming an ORR for nivolumab monotherapy of 21.5%, the sample size is chosen to detect a difference in ORR of 26.0% (ie, ORR = 47.5%) with 76% power at a 1-sided significance level of 0.10. The 95% CI of a 47.5% ORR (19 responders / 40 subjects) based on the exact probability method is 31.5%, 63.9%. The assumption of a nivolumab monotherapy ORR of 21.5% is based on the data from the nivolumab package insert.

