#### 3.4.1.7 Overall Survival

Overall survival (OS) is defined as the time from randomization (dose expansion) / the first dose of IP (dose escalation) until death due to any cause. A subject alive at the end of study or lost to follow-up will be censored for OS at the last date when the subject was known to be alive. OS is defined in months as follows:

OS (months) = (Date of death or censoring – Date of randomization (dose expansion) / the first dose of IP (dose escalation) + 1) / (365.25/12).

The median OS and its 95% CI will be estimated using the Kaplan-Meier method. For the expansion phase, the difference in OS between treatment groups will be tested for significance with a logrank test. The hazard ratio for the two treatment groups with two-sided 95% CI will be estimated by a Cox proportional hazard model controlling for the prespecified stratification factors as explanatory variables in the model. The proportion of subjects alive at 12 months and associated 95% CI will be estimated using the Kaplan-Meier method.

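### The PFS and OS log-rank tests name no strata although randomisation is stratified and the hazard ratio is adjusted; if the strata are prognostic, the test loses power and can disagree with the 95% CI beside it

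*SAP*

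**What the plan says.** SAP section 2.2 randomises the expansion phase 2:1 within strata: "Stratification factors will include the Memorial Sloan Kettering Cancer Center (MSKCC) risk group" (three levels) and PD-L1 expression (two levels, split at 1%). The maximum size is 40 on the combination and "up to 20 subjects in the nivolumab monotherapy arm".

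For PFS, section 3.4.1.6 states that "the difference in PFS between treatment groups will be tested for significance with a logrank test". The next sentence is "The hazard ratio for the two treatment groups with two-sided 95% CI will be estimated by a Cox proportional hazard model", with the stratification factors entered as covariates. Section 3.4.1.7 does the same for OS: "the difference in OS between treatment groups will be tested for significance with a logrank test", followed by the same adjusted Cox model.

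Neither section gives a level or sidedness for the test, and no other section makes the log-rank stratified. The only significance level in the SAP is in section 2.4, for ORR: "with 76% power at a 1-sided significance level of 0.10".

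**The concern.** The plan controls for the randomisation factors in the estimate but not in the test printed beside it. On a plain reading the log-rank gives the significance verdict and the Cox model only estimates.

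Stratified randomisation balances the arms on MSKCC and PD-L1. If these factors predict outcome, a test that ignores them uses a variance that does not credit that balance, and it compares mixed populations in which the treatment effect is diluted. The test then rejects too rarely, both under the null and under a real effect. The adjusted Cox model does not have this loss.

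The report could therefore show a non-significant p-value next to a 95% CI that excludes 1, with no stated rule for which one counts. That invites choosing between them after the data are seen.

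**Working it through.** **The plan's own figure.** The only powered comparison is ORR: 21.5% on 20 subjects against 47.5% on 40, one-sided 0.10.
- Pooled rate = (20 × 0.215 + 40 × 0.475) / 60 = 0.388.
- Null SE = √(0.388 × 0.612 × (1/20 + 1/40)) = 0.1335.
- Alternative SE = √(0.215 × 0.785/20 + 0.475 × 0.525/40) = 0.1211.
- z = (0.26 − 1.2816 × 0.1335) / 0.1211 = 0.73, so power is 76.9%, against 76% stated.

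The figure reproduces but does not bear on PFS or OS, for which the SAP gives no event number, hazard ratio or power.

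**Inputs from the SAP.** 60 subjects, 2:1; 3 × 2 = 6 randomisation cells; log-rank with no strata; Cox model with MSKCC and PD-L1 as covariates; two-sided 95% CI.

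**Assumptions, none given in the SAP.**
- Shares: MSKCC 35/50/15%, PD-L1 75/25%.
- Hazard multipliers: none; moderate (MSKCC 0.6/1/1.8, PD-L1 1.2/0.85); strong (MSKCC 0.45/1/2.5, PD-L1 1.4/0.75).
- Exponential times, common entry, permuted blocks of 6 within cells.
- Data cut at the 45th event (0.75 × 60).
- Test level two-sided 0.05.

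**Formulas.** Log-rank: Z = Σ(O − E) / √ΣV over risk sets pooled across strata. Cox: log hazard = log baseline + βg + γ₁M₁ + γ₂M₂ + γ₃P, where g is treatment, M₁ and M₂ are MSKCC indicators and P is PD-L1. The 95% CI is exp(b ± 1.96 se). Disagreement means that (log-rank p < 0.05) differs from (CI excludes 1).

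**Results at hazard ratio 0.5** (20,000 simulated trials per column; Monte Carlo standard error at most 0.5 points):

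| | Not prognostic | Moderate | Strong |
|---|---|---|---|
| Log-rank power | 62.8% | 55.9% | 47.3% |
| Adjusted CI excludes 1 | 62.8% | 62.5% | 61.6% |
| Test and CI disagree | 5.4% | 11.4% | 18.2% |
| – CI excludes 1, log-rank not significant | 2.7% | 9.0% | 16.2% |
| – the reverse | 2.7% | 2.4% | 2.0% |

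The rows are consistent: for moderate strata 9.0 − 2.4 = 6.6 = 62.5 − 55.9. A separate simulation of the same setting gave log-rank power of 62.9 / 56.6 / 46.9% and disagreement of 6.3 / 11.8 / 18.4%.

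**Sensitivity of the disagreement rate** (not / moderate / strong):
- Hazard ratio 0.75: 3.6 / 6.8 / 9.0%.
- Null: 1.8 / 3.1 / 4.4%.
- Hazard ratio 0.5 with 50% events: 4.9 / 8.7 / 13.1%.
- Hazard ratio 0.5 with shares 25/60/15% and 60/40%: 5.5 / 11.0 / 17.1%.

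The log-rank rejects under the null in 5.1 / 4.1 / 3.5%, so it is conservative and not inflated.

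**Testing the treatment term of the stated Cox model.** At hazard ratio 0.5 and 75% events, power is 64 / 64 / 63% (score test) or 64 / 63 / 61% (Wald test). The Wald test agrees with the Wald CI by construction, because |b/se| > 1.96 is the same event as the CI excluding 1. The score test agrees in about 99%. Null rejection was 5.2 to 5.8% here and 5.7 to 6.1% for the Wald CI in the 20,000-trial runs. It was 6.0 to 6.4% in a further simulation with random censoring and blocks of 3. A little of the power is owed to that slight excess.

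**Stratified alternatives at hazard ratio 0.5.**
- Log-rank stratified by MSKCC alone: power 60.7 / 59.3 / 56.4%. With a Cox model stratified the same way, test and CI disagree in at most 1.1%. Paired with the Cox model as now written, disagreement stays at 5.5 / 7.0 / 9.3%.
- Log-rank stratified on all six cells (simulation with random censoring and blocks of 3, own prognostic settings none / weak / moderate / strong): power 58 / 57 / 54 / 52%, against 63 / 59 / 50 / 39% unstratified. It still disagrees with the adjusted CI in 10 to 11%.

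**The case against.** The strongest reply is that nothing important rests on these tests. The expansion objective is antitumour activity "as based on investigator assessed response using Response Evaluation Criteria in" Solid Tumors (section 2.1.1), the sample size is set on ORR (section 2.4), and futility and Go/NoGo use the ORR difference (section 4). A marginal test beside an adjusted estimate is also a defensible pairing. This stands, and it limits the weight of the point. It does not remove the mismatch, because both sections promise a formal test.

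The size also rests on prognostic strengths that the SAP does not give. Net of the 5.4% baseline, the excess disagreement at hazard ratio 0.5 is 11.4 − 5.4 = 6.0 points (moderate) and 18.2 − 5.4 = 12.8 points (strong). It is smaller at weaker effects. This stands too, which is why a range is shown.

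Four stronger readings are tempting, and the SAP does not support them:
- *The test is invalid or inflates type I error.* The error runs the other way.
- *Power is certainly lost.* With non-prognostic strata there is no loss.
- *One-sided 0.10 applies to PFS and OS.* It is stated only for the ORR sample size, and section 3.1 makes two-sided 95% intervals the default. The level for these tests is simply not stated.
- *The log-rank has to be stratified.* The Cox model already in the plan uses both factors and can supply the test.

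**Conclusion.** The point holds as a minor one. For both PFS and OS, the log-rank names no strata while the randomisation and the hazard-ratio model use MSKCC and PD-L1, and no test level is given.

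If the strata are prognostic, the test is conservative. At a hazard ratio of 0.5 with 60 subjects and 45 events, it loses roughly 6 points of power (moderate strata) to 16 points (strong strata) from about 63%, and contradicts the adjusted CI in about 12 to 18% of trials instead of 5 to 6%. Prognostic strength, stratum shares, hazard ratio, event fraction and test level are all assumptions. The text mismatch itself needs none of them.

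**What to change.** In sections 3.4.1.6 and 3.4.1.7, take the p-value from the treatment term of the model already specified ("Cox proportional hazard model controlling for the prespecified stratification factors as explanatory variables in the model"). Name the score or the Wald test, and state two-sided 0.05 to match the 95% CI. Keep the unstratified log-rank as a sensitivity analysis.

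Cost: a sentence or two in each section, and no new data. The downsides are a null rejection rate slightly above nominal (5.2 to 6.4% across the simulations) and reliance on proportional hazards and on the covariate form of the model.

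An acceptable alternative is a log-rank and a Cox model both stratified by MSKCC alone, at the same stated level. Its costs are:
- PD-L1 leaves the main analysis.
- If MSKCC is not prognostic, about 2 power points are lost (62.8 to 60.7%; with 50% events, 48.6 to 47.5%).
- The CI is less sharp: it excludes 1 in 59.6 / 58.2 / 55.4% of trials instead of 62.8 / 62.5 / 61.6%, although its null rate is 4.6 to 4.9%.
- Levels become sparse after an early futility stop. Under the assumed shares, some MSKCC level has no nivolumab subject in 16 to 19% of trials at 30 subjects and 6 to 7% at 42, against under 2% at 60. SAP Table 4.1 puts interim stopping at 77% with no effect and 9% with a 20-point effect.

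Do not stratify on all six cells: at 60 subjects some cell has no nivolumab subject in 32 to 50% of simulated trials, and power falls when the strata are weakly or not prognostic.

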#### **CENSORING OF PFS**

Table 3.2 Summary of Censoring Guidelines for Efficacy Endpoints

| Situation   | Date of PD/Death or Censoring   | PFS Outcome                          |
|---|---|--------------------------------------|
| Documented Progressive Disease (PD)   | Date of earliest sign of PD   | Event                                |
| Death prior to second scheduled post-baseline disease assessment or after an adequate post-baseline disease assessment  | Date of death   | Event                                |
| No PD or death at time of analysis or lost to follow-up   | Date of last adequate progression-
free disease assessment   | Censored                             |
| Death or PD immediately after ≥ 2 consecutive missed or non-evaluable disease assessments   | Date of randomization (dose expansion) / the first dose of IP (dose escalation) or last progression-free disease assessment prior to missed or non-evaluable assessments, whichever occurred last | Censored                             |
| Initiation of subsequent anticancer treatment   | Date of last adequate progression-
free disease assessment prior to
initiation of subsequent anticancer
treatment  | Censored for
Sensitivity Analyses |
| No tumor assessment at baseline and no evidence of PD at first post-baseline disease assessment, OR  No tumor assessment post-first dose, and no death prior to second scheduled post-baseline disease assessment | Date of randomization (dose expansion) / the first dose of IP (dose escalation)   | Censored                             |

PD = progressive disease; PFS = progression-free survival

Subjects having missing lesion data at baseline or no disease assessments post-first dose will have PFS censored at the date of randomization (dose expansion) / the first dose of IP (dose

escalation) unless the subject dies prior to the second scheduled post-baseline disease assessment in which case the death date will qualify as a PFS event.

If a subject has two or more consecutive completely missed or non-evaluable assessments followed immediately by death or an assessment showing radiologic disease progression, then the subject will be censored for PFS. PFS will be censored at the date of randomization (dose expansion) / the first dose of IP (dose escalation) or the last progression-free disease assessment prior to the missed or non-evaluable assessments, whichever occurred last. If a subject has two or more consecutive missed or non-evaluable assessments followed by an assessment showing no radiologic disease progression, then the assumption will be that the subject did not progress during the missed or non-evaluable assessments. Two or more consecutive assessments is defined as  $\geq 17$  weeks (two disease assessments as per protocol plus a 1 week visit window to allow for a late assessment) after the last evaluable post-baseline disease assessment.

Subjects remaining on study without radiologic disease progression or death at the time of analysis will be censored for PFS at the date of their last adequate disease assessment. An adequate assessment is one that has recorded measurements for all target lesions and statuses for all non-target lesions defined at baseline (ie, the last non-missing or non-evaluable disease assessment). Additionally, a sensitivity analysis may be performed censoring PFS at the date of the last progression-free disease assessment prior to initiation of subsequent anticancer treatment.

#### 3.4.1.7 Overall Survival

Overall survival (OS) is defined as the time from randomization (dose expansion) / the first dose of IP (dose escalation) until death due to any cause. A subject alive at the end of study or lost to follow-up will be censored for OS at the last date when the subject was known to be alive. OS is defined in months as follows:

OS (months) = (Date of death or censoring – Date of randomization (dose expansion) / the first dose of IP (dose escalation) + 1) / (365.25/12).

The median OS and its 95% CI will be estimated using the Kaplan-Meier method. For the expansion phase, the difference in OS between treatment groups will be tested for significance with a logrank test. The hazard ratio for the two treatment groups with two-sided 95% CI will be estimated by a Cox proportional hazard model controlling for the prespecified stratification factors as explanatory variables in the model. The proportion of subjects alive at 12 months and associated 95% CI will be estimated using the Kaplan-Meier method.

#### 3.4.1.8 Change from Baseline in Tumor Sizes

The percent change from baseline in target lesion sum of diameters (longest for non-nodal lesions, short axis for nodal lesions) will be calculated at each post-baseline disease assessment with recorded measurement for all target lesions defined at baseline. The percent change from baseline in target lesion sum of diameters is defined as follows:

100 \* ( $\Sigma$  Diameters at DA X -  $\Sigma$  Diameters at BL) / ( $\Sigma$  Diameters at BL).

The percent change from baseline in target lesion sum of diameters will be presented by subject using spider plots. The best percent change from baseline in target lesion sum of diameters is defined as the largest reduction or smallest increase (in the case where a reduction does not occur) from baseline observed over all post-baseline disease assessments. The best percent change from baseline will be presented using waterfall plots. Target lesion measurements and sum of diameters will be listed by disease assessment and subject.

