## 2.2.1 Treatment Regimen

Subjects will be treated in either the dose-escalation or dose-expansion phase. MEDI0680, durvalumab and nivolumab will be administered via IV infusion. In dose-escalation phase, subjects will remain on treatment for up to 12 months. In the dose-expansion phase, subjects will remain on treatment until unacceptable toxicity, confirmed PD, or development of other reason for treatment discontinuation.

In the dose-escalation phase only, subjects who achieve and maintain DC (ie, CR, PR, or stable disease [SD]) through the end of the 12-month treatment period will enter follow-up. During the first 12 months of follow-up, if the subject has PD, the subject may be re-administered MEDI0680 and durvalumab for up to another 12 months with the same treatment guidelines followed during the initial 12-month period if the subject fulfills the criteria for re-treatment in the setting of PD, has not received other anticancer treatments for their disease, and does not meet any of the IP discontinuation criteria as described in the protocol. Only 1 round of re-treatment will be allowed.

Nivolumab will be administered according to the package insert guidelines.

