#### 3.4.1.1 Best Overall Response

Best overall response (BOR) will be based on all post-baseline disease assessments that occur prior to the initiation of subsequent anticancer treatment. If re-treatment is permitted following an initial disease progression, a BOR will be reported separately for the re-treatment period. BOR will be summarized with the number and percentage of subjects for

the following categories: complete response (CR); partial response (PR); stable disease (SD); progressive disease (PD); and non-evaluable (NE).

At least 6 weeks from randomization (dose expansion) / the first dose of IP (dose escalation) first dose of IP must elapse without a radiological disease progression in order to assign a best overall response of SD. The definition of 6 weeks will allow for the protocol-defined disease assessment window of 3 days. Confirmation of PR and CR is required and must occur no fewer than 4 weeks after initial documentation of PR or CR. If a PR or CR that is pending confirmation is designated at an assessment followed by 1 or more non-evaluable assessments for CR or 1 or more non-evaluable assessments or assessments of SD for PR, response may be confirmed thereafter. Confirmation of PD is required in the dose escalation phase, but not the dose expansion phase. A confirmed PD will be a documented occurrence of a PD that is confirmed by a consecutive repeat assessment no fewer than 4 weeks later. A PD that occurs without follow-up scans to provide confirmation or only non-evaluable follow-up scans will also be considered a "confirmed" PD.

Concordance/discordance of disease assessment by investigator and derived disease assessment will be summarized in frequency table.

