## 3.3.5.3 Locoregional therapy

Any subject receiving locoregional therapy, including surgery, while on study that directly affects one or more of the target lesions selected at baseline and/or new lesions included in tumor burden will be identified. A subject with a subsequent response or SD/irSD will be considered to be non-evaluable at all disease assessments that occur on or after the date of locoregional therapy. Otherwise, the subject will be assessed ignoring the locoregional therapy.

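### Best percent change in tumor size has no cut-off at subsequent anticancer treatment and does not separate the re-treatment course, unlike best overall response

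*SAP*

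**What the plan says.** Change from baseline in target lesion sum of diameters is one of the efficacy endpoints listed in SAP Section 3.4.1. Section 3.4.1.8 calculates it "at each post-baseline disease assessment with recorded measurement for all target lesions defined at baseline" and takes the best value as the "largest reduction or smallest increase (in the case where a reduction does not occur) from baseline observed over all post-baseline disease assessments". It is shown in spider plots, waterfall plots and listings. The section sets no end date, does not mention subsequent anticancer treatment or re-treatment, and does not refer to other sections.

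Four other places bear on the same scans:

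- **BOR (3.4.1.1)** uses "all post-baseline disease assessments that occur prior to the initiation of subsequent anticancer treatment". Where re-treatment after progression is permitted, "a BOR will be reported separately for the re-treatment period".
- **PFS (3.4.1.6)** counts progression "regardless of whether the subject receives subsequent anticancer therapy prior to progression". Table 3.2 censors at subsequent treatment for sensitivity analyses only.
- **Re-treatment (2.2.1)** exists in dose escalation only: after progression in follow-up, "the subject may be re-administered MEDI0680 and durvalumab for up to another 12 months". Table 3.1 defines a Re-treated Population, to be presented separately if it is large enough.
- **Locoregional therapy (3.3.5.3)**: if it directly affects a target lesion, a subject with a later response or stable disease "will be considered to be non-evaluable at all disease assessments that occur on or after the date of locoregional therapy". In all other cases the therapy is ignored.

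**The concern.** BOR and best percent change rest on the same target lesion measurements, yet the SAP gives them different assessment windows and no reason for the difference. BOR stops when another anticancer therapy starts. The waterfall bar does not.

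A subject whose BOR is stable disease on study drug could therefore appear with a deep reduction that occurred under a different therapy. In dose escalation, a subject who progressed and was re-treated could have the single best value taken from the second course, although the SAP keeps the two courses apart for BOR.

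Waterfall plots are commonly read as a picture of drug activity. In an open-label randomized expansion phase they will also be compared by eye between arms, and later therapy could differ between the arms. What is at stake is how faithful that picture is, and whether it agrees with the response table beside it.

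**Working it through.** The SAP states no figure for tumor-size change, so there is none to reproduce. The check is a comparison of rules, followed by an illustration.

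**1. The two windows side by side**

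| Rule | BOR (3.4.1.1) | Best percent change (3.4.1.8) |
|---|---|---|
| Stops at subsequent anticancer treatment | Yes | No |
| Re-treatment reported separately | Yes | Not stated |
| Filter on individual scans | Response derivation, including non-evaluable | All baseline target lesions measured |

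**2. Can such scans be in the data?** Yes. The main PFS definition counts progression after subsequent therapy, and Table 3.2 censors there only for sensitivity analyses. The main PFS analysis can therefore use scans taken under another therapy. How often they occur is not stated.

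**3. Direction of the error.** Let A be a subject's measured assessments before subsequent therapy and B those after it. Where A is not empty, min(A and B together) ≤ min(A). Adding B leaves the bar unchanged or makes it look better; it cannot make it look worse. A subject with no measured assessment in A would gain a bar that the BOR window would not supply. The same inequality applies when B is a second course of study drug.

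**4. Illustration for one subject (all values assumed).** Baseline sum 100 mm; 95 and 112 mm before subsequent therapy; 85 and 60 mm after it. The formula in 3.4.1.8 is 100 × (sum at assessment − baseline sum) / baseline sum.

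- 95 mm: 100 × (95 − 100)/100 = −5%
- 112 mm: 100 × (112 − 100)/100 = +12%
- 85 mm: 100 × (85 − 100)/100 = −15%
- 60 mm: 100 × (60 − 100)/100 = −40%

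Best change as written: −40%. With the BOR window: −5%. The rise from 95 to 112 mm is 17/95 = 17.9%, below the 20% needed for target lesion progression. With no other sign of progression and the six-week minimum met, this subject's BOR would be stable disease, while the waterfall bar would lie beyond a 30% reduction.

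**5. How many bars (assumed shares).** Let q be the share of subjects whose smallest sum falls after subsequent therapy. The SAP gives no q. Affected bars = n × q.

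| q (assumed) | n = 20 (nivolumab) | n = 40 (combination) | n = 60 (both) |
|---|---|---|---|
| 2% | 0.4 | 0.8 | 1.2 |
| 5% | 1.0 | 2.0 | 3.0 |
| 10% | 2.0 | 4.0 | 6.0 |

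These are bars that change at all. Fewer would cross a 30% reduction.

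**6. What depends on the endpoint.** Section 3.4.1.8 gives it no test, confidence interval or formal arm comparison. ORR (3.4.1.2) is built on BOR, which already stops at subsequent therapy. The Go/NoGo and futility rules (Section 4) use CR or PR, not percent change.

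**The case against.** The strongest case against has five parts.

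**Re-treatment is study drug.** A reader might infer that shrinkage during re-treatment is another therapy's effect credited to the study drugs. Section 2.2.1 does not support that: re-treatment uses MEDI0680 and durvalumab, and only in dose escalation, so it cannot distort the randomized comparison. The Re-treated Population also gives it a possible separate summary. This stands. What remains is that the main display can merge two courses that BOR keeps apart.

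**Locoregional therapy is largely covered.** A reader might infer that the SAP lets shrinkage after local treatment count freely. Section 3.3.5.3 makes later response or stable disease non-evaluable, and step 3 of the target lesion algorithm in 3.3.5.1 returns a non-evaluable response when an intervention on a target lesion is recorded, unless the progression criterion in step 2 is already met. This mostly stands. The residue is that 3.4.1.8 filters on recorded measurements, not on evaluability, and does not refer to 3.3.5.3.

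**Waterfall and BOR need not agree.** BOR also reflects confirmation, new lesions and non-target lesions, so some disagreement is legitimate. True, but a difference caused only by the assessment window is avoidable and is not explained.

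**The frequency is unknown.** The scan schedule after new therapy is a protocol matter not visible here. This stands, and is why no size is claimed beyond assumed ranges.

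**The filter could sit in the statistical programming plan.** Section 1 leaves table templates and specifications to that document. But 3.4.1.8 is not silent: it states that all post-baseline assessments are used, and a filter placed elsewhere would contradict it.

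**Conclusion.** The point holds in a limited form. Section 3.4.1.8 has no cut-off at subsequent anticancer treatment and does not separate re-treatment, whereas 3.4.1.1 does both. Followed literally, the rule can move existing waterfall bars only toward more apparent activity. Spider plots have no such one-way bias, but their lines would run on into another therapy without a stated limit.

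The number of subjects affected cannot be derived from the SAP. The range of about 1 to 6 of 60 bars rests on assumed shares of 2% to 10%, and the −40% against −5% contrast on assumed measurements.

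A reader might infer that the trial's efficacy conclusions are inflated. The document does not support that: the endpoint is descriptive, and ORR, the significance tests and the Go/NoGo decisions do not use it. Nor does the document show that the arms would be affected differently; with open-label treatment that is possible, not established. This is a minor improvement that should be made because it is cheap.

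**What to change.** Add to Section 3.4.1.8, in substance:

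- Best percent change and the spider plots use only assessments before the start of subsequent anticancer treatment, the same window as BOR in 3.4.1.1.
- In dose escalation, assessments from the re-treatment period are presented separately and do not contribute to the initial course.
- For locoregional therapy, 3.3.5.3 applies: an assessment that is non-evaluable under that rule does not supply the best percent change.

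The third item should be a cross-reference, not a blanket exclusion of every scan after locoregional therapy. Such an exclusion would conflict with 3.3.5.3, which ignores the therapy unless a response or stable disease follows, and would discard growth data that the SAP keeps.

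The cost is a short addition to one section and one data filter. No new data should be needed: the start of subsequent treatment is already required for the BOR window and for the PFS sensitivity analysis in Table 3.2, and Section 3.3.3 already summarizes that treatment.
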